Health Care Utilization	Caregiver interview – health care utilization survey	Baseline, each follow-up
	Review of medical chart and pharmacy records	Conclusion of Study
Airway Inflammation	Objective measurement: FeNO	Baseline, 7 month follow-up
Pulmonary Function	Spirometry	Baseline, 7 month follow-up
Functional Outcomes		

School Absenteeism	Caregiver interview School record review	Baseline, each follow-up Conclusion of study
Quality of Life	Caregiver interview-PACQLQ	Baseline, each follow-up
Potential Mediators		
Adherence	Caregiver interview-Horne Adherence Scale	Baseline, each follow-up
Communication with Providers	Caregiver interview-PEPPI	Baseline, 7 month follow-up
Satisfaction with Medical Care	Caregiver interview-PSQ-18	Baseline, 7 month follow-up
Independent Variables		
Demographic, Medical Variables	Caregiver interview	Baseline
Caregiver Depression*	Caregiver interview-CES-D	Baseline, 7 month follow-up
Environmental Allergens	Environmental survey	Baseline
Secondhand Smoke	Caregiver interview Salivary Cotinine measurement	Baseline, each follow-up Baseline, 7 month follow-up
Process Evaluation		
Training of School Nurses, CTAs, and Providers	Time to train nurses to deliver DOT with proper inhaler technique, train CTAs for asthma assessments, and providers for reinforcement of guideline based asthma care	Ongoing tracking log
Medication Delivery to School	Tracking log of days required to deliver medications to school and home and initiate DOT; both at beginning of the study and for follow-up adjustments	Ongoing tracking log
Percent of Days Children Receive Medications via DOT	Nurse medication administration and video supported DOT records	Collected at the end of the school year
RE-AIM Metrics		
Reach,	Response rate, participant characteristics	Ongoing tracking log, screening/baseline
Effectiveness,	Primary analysis (symptoms, absenteeism, quality of life)	Conclusion of study
Adoption, Implementation, Maintenance	Semi-structured interviews: parents, nurses, administrators, PCPs, specialists Perceived Attributes scale (for school nurses, health aides, and administrators)	Conclusion of study Conclusion of study

	Medical record review Response rate and attrition tracking	Tracking log
--	---	--------------

**All Families will be provided a list of local mental health resources at the beginning of this study.*

Fraction of Exhaled Nitric Oxide (FeNO):

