For the primary outcome analysis, the time-course of treatment effect on SFD during the follow-up period will be evaluated using a linear mixed model (LMM) accounting for repeated measures within each subject to test the intervention effect of TEAM-UP over time, with SFD as the dependent variable, and intervention group and group by time interaction as independent variables.⁷⁰ The treatment effect will be regarded as fixed and the subjects as the random effect, with appropriate variance covariance structure specified. Interaction effects between intervention and follow-up periods are included to catch possible differences in how SFD changes over time between intervention groups. Post treatment effects and maintenance gain from short to long term will be assessed by specifying appropriate linear contrasts. Baseline SFD and factors that differentiate between groups will be included as covariates. Model fitting statistics such as Information Criteria and difference in log likelihood will be used for model selection. Standard measures such as residual plots will check goodness-of-fit of the regression model assumptions and identify outliers. We will calculate intraclass coefficient (ICC) within providers (specialist and PCP); if autocorrelation is significant, provider will be included as another level of random effect in the mixed model to account for the nested data structure. If the outcome measure violates the normal assumption required by LMM, we will evaluate the intervention effect using Generalized Estimating Equations (GEE).⁷¹ By specifying marginal mean effects of independent variables on the outcome variable, GEE offers consistent and robust estimates but does not require specification of a fully parametric distribution. Other continuous outcomes (days/nights with symptoms, quality of life, etc.) will be analyzed similarly. Discrete outcomes will be analyzed by fitting Generalized Estimating Equation model. Appropriate link functions and response probability distributions will be specified.

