We will also consider whether certain process measures from our conceptual framework (guideline-based corrective actions, adherence, patient/provider communication, satisfaction with care) act as mediators in the relationship between the intervention and outcomes.⁷² Thus we will estimate both the direct intervention effect on outcomes, as well as the indirect effect through mediators. For each purported mediator, we will use structural equation models (SEM)⁷³ to model its relationship to treatment and primary outcome. Maximum Likelihood (ML) will be used for estimation. Goodness-of-fit will be assessed in a two-level process. In the first level, the fit of the unrestricted model will be tested using standard diagnostic measures for linear regression. In level two, the appropriateness of assumption of the proposed structural equation model will be investigated by testing this model against the unrestricted model. The following indicators will be used:⁷⁴ (a) Comparative Fit Index (CFI), (b) Non-Normed Fit Index and (c) Root Mean Square Error of Approximation.⁷⁵ We will use chi-square statistics for the structural invariance tests to determine effect modifiers. These analyses will aid in our understanding of pathways by which TEAM-UP impacts outcomes.

The primary analyses will include all randomized subjects. Substantial attention will be invested in participant retention; reasons for any withdrawals that may occur will be documented. Missing data patterns will be examined by comparing subjects who discontinued with those who remained in the study. Inference based on the proposed methods GEE and/or LMM is valid provided that missing data follows the missing completely at random (MCAR) assumption. However, if the occurrence of missing data depends on the observed response but is independent of unobserved data (MAR), weight GEE (WGEE) will be used. Sensitivity analysis to the MAR assumption will also be carried out by modeling the between-group difference using WGEE.^{76,77} Separate secondary per protocol analyses will be performed and interpreted with caution.

Cost Effectiveness Analysis:

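### The mediation models name no baseline SFD, baseline mediator level or co-mediator, so a mediator with no effect of its own can be declared a pathway

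*Combined protocol and SAP*

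**What the plan says.** The mediation plan is one paragraph of the Primary Analysis section of the combined protocol and SAP. It names four candidate mediators: "guideline-based corrective actions, adherence, patient/provider communication, satisfaction with care". It states the targets: "we will estimate both the direct intervention effect on outcomes, as well as the indirect effect through mediators". The method is given as "For each purported mediator, we will use structural equation models", used "to model its relationship to treatment and primary outcome". Estimation is by maximum likelihood. Fit is assessed in part by "testing this model against the unrestricted model", with three fit indices. The stated use is: "These analyses will aid in our understanding of pathways by which TEAM-UP impacts outcomes".

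The paragraph mentions no covariates, no co-mediator and no sensitivity analysis for confounding of mediator and outcome. The sentence "Baseline SFD and factors that differentiate between groups will be included as covariates" stands in the preceding paragraph and belongs to the linear mixed model for the primary outcome.

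The Measures table schedules adherence ("Caregiver interview-Horne Adherence Scale") at baseline and each follow-up, and communication (PEPPI) and satisfaction (PSQ-18) at baseline and 7 months. Symptom severity is also taken at baseline. The data for baseline adjustment of these three mediators and of SFD therefore already exist.

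**The concern.** Treatment is randomised; the mediators are not. The effect of treatment on a mediator is protected by design, but the association between mediator and SFD within an arm is observational. Two things can create that association when the mediator itself does nothing.

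- **Stable family traits.** Adherence, communication and satisfaction are all caregiver reports, and SFD also comes from caregiver interview. Families that report well on one at every visit may report well on the other.
- **A correlated active mediator.** If an inert mediator moves together with an active one within arm, a model without the active one gives its effect to the inert one.

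In both cases, if TEAM-UP also shifts the inert mediator, the product of the two paths is non-zero and a pathway is declared. What is at stake is the published account of how TEAM-UP works, which is the declared purpose of this analysis. The comparison of SFD between arms does not depend on it.

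**Working it through.** The plan gives no power, effect size or correlation for the mediation analysis, so there is no planned figure to reproduce. From the Sample Size and Power Justification come 150 per group, an SFD SD of 3.6, a within-subject correlation of 0.3 and a difference of 0.8 SFD. Four follow-ups are planned. Everything else is assumed and shown as a range. A pathway is counted as declared when both paths are significant at two-sided 5%.

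**A. Family trait, no active mediator.** Let the mediator have ICC 0.5 and let ρ be the correlation between its stable part and that of SFD. In units of one visit's SFD SD:

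- Variance of the mean of four visits: (1 + 3 × 0.3)/4 = 0.475.
- Within-arm covariance of mediator and mean SFD: k = ρ√(0.5 × 0.3) = 0.387ρ.
- Correlation: 0.387ρ/√0.475 = 0.562ρ.
- Treatment-to-mediator path for a 0.4 SD shift: z = 0.4/√(2/150) = 3.46, power 93%.
- Mediator-to-SFD path: z = r√297/√(1 − r²).
- False indirect effect in SFD: 0.4 × k × 3.6.

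With baseline mediator and baseline SFD added, r becomes the partial correlation. The covariances of the two baselines with the mediator are (0.5, k), and with mean SFD (k, 0.3); the two baselines have covariance k. At ρ = 0.4, k = 0.155. The residual covariance is then 0.0556 and the residual variances are 0.744 and 0.373, so r = 0.0556/√(0.744 × 0.373) = 0.105. The treatment-to-mediator path gains power: z = 4.0, 98%.

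| Covariates | ρ | r | z, mediator to SFD | Power of that path | False pathway | False indirect effect (SFD) |
|---|---|---|---|---|---|---|
| none | 0.2 | 0.112 | 1.95 | 50% | 46% | 0.11 |
| none | 0.3 | 0.169 | 2.95 | 84% | 78% | 0.17 |
| none | 0.4 | 0.225 | 3.98 | 98% | 91% | 0.22 |
| both baselines | 0.2 | 0.051 | 0.88 | 14% | 14% | 0.05 |
| both baselines | 0.3 | 0.078 | 1.33 | 27% | 26% | 0.08 |
| both baselines | 0.4 | 0.105 | 1.82 | 44% | 44% | 0.11 |

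Against 0.8 SFD, the unadjusted false effect is 0.11/0.8 = 14% to 0.22/0.8 = 28%. Repeated simulations of this set-up gave 44–91% with no baseline covariates, 30–82% with baseline SFD only, and 13–45% with both. At ρ = 0 the rate is about 5%. With no treatment shift it is 5% or less.

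**B. Omitted active mediator.** With unit residual SDs, the false indirect effect is a₂ × b₁ × r. Here a₂ is the shift in the inert mediator, b₁ the SFD effect of the active one, and r their within-arm correlation. Take a₂ = 0.5; the time-averaged SFD SD is 3.6 × √0.475 = 2.48; 300 children, 3000 runs:

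- b₁ = 0.8, r = 0: 0.00; declared in 5%.
- b₁ = 0.8, r = 0.3: 0.5 × 0.8 × 0.3 = 0.12 SFD (15% of 0.8); declared in 40%.
- b₁ = 0.8, r = 0.5: 0.20 SFD (25%); declared in 80%.
- b₁ = 1.6, r = 0.3 and 0.5: 0.24 and 0.40 SFD (30% and 50%); declared in 92% and 99%.
- a₂ = 0: 0.00; declared in 2–5%.

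A model that also holds the active mediator and baseline SFD returns 0.00 and about 5% in the cases with a₂ = 0.5.

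**C. The same data from a causal chain.** Now let the second mediator act through the first, for example communication improving adherence. With a 0.4 SD shift and b = 0.3 SD per SD, its true indirect effect is 0.4 × r × 0.3 = 0.036, 0.048 and 0.060 SD at r = 0.3, 0.4 and 0.5. Single-mediator models estimate 0.036, 0.049 and 0.059 and detect it in 31%, 51% and 69% of trials. Those rates match the 32%, 51% and 68% for an inert mediator with the same inputs. The all-mediator model estimates about zero and detects it in 5%. The two structures imply the same covariances, so the data cannot separate them.

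**The case against.** The strongest reply is that silence is not exclusion. A reader might infer that each model contains only treatment, one mediator and SFD. The documents do not say so, and the fit plan points the other way. A three-variable model with direct and indirect paths has 3 × 4/2 = 6 moments and 6 parameters, hence 0 degrees of freedom, and a test against an unrestricted model would be empty. The contents are unspecified rather than fixed at three variables. That stands, but the adjustment still needs to be written in, since it is stated for the mixed model and not for this one.

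A second reply is that single-mediator models are legitimate. A reader might infer that one joint model is simply the right analysis and should replace them. Part C shows why that does not follow: the joint model assumes no causal ordering among mediators and removes a real upstream effect. The plan refers to a conceptual framework, but the text gives no ordering. This reply stands, and it makes the choice a trade-off to be declared.

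Third, the bias is conditional. That one programme targets all four mediators creates no bias by itself, because treatment is in the model. Treatment must move the inert mediator, and there must be a within-arm or baseline link to SFD. This also stands.

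Finally, a reader might infer that Objectives 7 and 8 (cost-effectiveness and implementation) would rest on these models. The Cost Effectiveness Analysis and Process Evaluation sections give those objectives their own methods, and neither uses the mediation models.

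**Conclusion.** The point holds as a gap in a secondary, explanatory analysis. As written, the plan does not commit to the baseline terms that would reduce confounding of the mediator-to-SFD path, although the measurements are scheduled. Under the assumptions in part A, a mediator with no effect is declared a pathway in about 45–90% of trials without baseline covariates and about 13–44% with both baselines. Adjustment therefore removes much of the problem but not all of it. The rates rest on assumed ICC, trait correlation and shift, none of which the documents give, and the problem disappears when treatment does not move the mediator or when neither link exists.

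The co-mediator part is weaker. A single-mediator indirect effect may include pathways shared with correlated mediators, but those may be real upstream effects, so no single model settles the question. The primary SFD test is unaffected.

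**What to change.** Amend the mediation paragraph of the Primary Analysis section along these lines:

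- Include baseline SFD, and the baseline value of each mediator collected at baseline (adherence, communication, satisfaction), as covariates in both the mediator equation and the outcome equation.
- Report a model with all mediators and correlated residuals alongside the single-mediator models. State that a single-mediator indirect effect may include pathways shared with correlated mediators, and that the joint model assumes no causal ordering among them and would remove a true upstream effect.
- Add a sensitivity analysis for unmeasured mediator-outcome confounding, because baseline adjustment reduces it without removing it.

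The cost is SAP wording and slightly more analysis, with no new data, visits or children. Joint-model estimates are less precise when mediators are strongly correlated. In the worst case tried (correlation 0.5, path 0.2 SD per SD), detection of a true mediator fell from 88% to 75%; with a path of 0.3 it was almost unchanged, at 93% against 92–93%.

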The overall goal of this project is to test a novel school-based program that links our effective school-based, primary care directed asthma management program with specialist-supported care for children requiring Step 3 or higher care. In partnership with caregivers and PCPs, specialist care will be facilitated via telemedicine, with management based on a tiered guideline-based stepwise approach. We will link children to existing community resources and will use school-based and/or video supported DOT to ensure adherence to therapies. This study includes a 2-group randomized trial to test TEAM-UP (***(Telemedicine Enhanced Asthma Management - Uniting Providers)***). All enrolled children (ages 4-12 yrs.) will be referred to their PCP for initiation of preventive asthma medication. Children randomly assigned to TEAM-UP will also have a telemedicine visit with a specialist provider after 4 weeks of initiating DOT as well as 2 follow-up visits to ensure optimal response to treatment. Collaboration with the PCP and the child's medical home will occur throughout the study period. We will enroll 360 children over four years from schools and primary care offices. We will assess the effectiveness of the program in reducing morbidity and improving guideline-based asthma care (primary outcome: symptom-free days at 3, 5, 7, and 12 months). At the study's completion, the effectiveness of this novel system of care will be better defined as a sustainable means to improve care and reduce morbidity for the highest risk children with difficult to control asthma. A subset of children (approximately 10-30 teens) ages 12-16 years will be enrolled to test the feasibility of TEAM-UP in older children.

Study Design:

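### In its plain reading, each single-mediator structural equation model has no degrees of freedom, so the planned fit checks cannot detect misfit and nothing planned examines mediator-outcome confounding

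*Combined protocol and SAP*

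**What the plan says.** The mediation paragraph under Primary Analysis names four process measures as possible mediators: guideline-based corrective actions, adherence, patient-provider communication and satisfaction with care. It states: "Thus we will estimate both the direct intervention effect on outcomes, as well as the indirect effect through mediators". One model is fitted per mediator, "to model its relationship to treatment and primary outcome", and "Maximum Likelihood (ML) will be used for estimation".

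Fit is judged at two levels. First: "In the first level, the fit of the unrestricted model will be tested using standard diagnostic measures for linear regression". Second: "the appropriateness of assumption of the proposed structural equation model will be investigated by testing this model against the unrestricted model", with CFI, the Non-Normed Fit Index (NNFI) and RMSEA as indicators.

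The paragraph gives no path diagram, visit, covariate, latent structure, restriction, degrees of freedom or fit cutoff. Elsewhere, the Study Overview defines the "primary outcome: symptom-free days at 3, 5, 7, and 12 months". In the Measures table, adherence ("Caregiver interview-Horne Adherence Scale") is taken at baseline and every follow-up. Communication and satisfaction are taken at baseline and 7 months. The one sensitivity analysis described under Primary Analysis concerns missing data.

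**The concern.** A test of a proposed model against the unrestricted model is informative only if the proposed model restricts something. Here the text asks for both a direct and an indirect path and names three variables, which leaves nothing restricted. The step presented as the check on the model's assumptions would then return perfect fit for any data.

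The assumption that carries a mediation claim is that no unmeasured factor drives both mediator and outcome. Treatment is randomised; the mediator is not. The risk is plausible in this trial. Families know their allocation, and adherence, communication, satisfaction and symptoms are all reported by the caregiver at interview. Communication and satisfaction are measured after baseline only at 7 months, so the 3- and 5-month symptom-free days (SFD) precede them. A shared cause such as family engagement could produce an apparent pathway. Level-one regression diagnostics do not address that either.

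**Working it through.** The plan states no degrees of freedom, so there is no figure of its own to reproduce.

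**Inputs.** From Sample Size and Power Justification: 150 children per group and an SD of SFD of 3.6. From the mediation paragraph: treatment X, one mediator M, the outcome Y, direct and indirect effects both estimated. Assumed here: no effect of M on Y, a shift in M due to TEAM-UP of 0.5 or 0.3 SD, and a residual correlation between M and Y of 0.1, 0.2 or 0.3.

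**Step 1: degrees of freedom in the plain reading.** The equations are M = aX + e1 and Y = c'X + bM + e2.
- Variances and covariances of three variables: 3 × 4 / 2 = 6.
- Free parameters: a, b, c', var(X), var(e1), var(e2) = 6.
- Degrees of freedom: 6 − 6 = 0.

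In 4,000 simulated datasets of 300 children the largest chi-square was 2.7e-13, which is rounding error. The model with mediator and outcome reversed fitted equally well. CFI is trivially 1. NNFI and RMSEA become 0/0, conventionally printed as 1 and 0.

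**Step 2: other readings.**

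| Specification | df |
|---|---|
| Baseline SFD in both equations | 0 |
| One mediator, four SFD visits, all paths and residual covariances free | 0 |
| Direct path fixed at zero (conflicts with estimating the direct effect) | 1 |
| Baseline SFD in the outcome equation only | 1 |
| Baseline SFD and baseline mediator, each predicting only its own follow-up | 2 |
| Autoregressive SFD at four visits, mediator to 12-month SFD only | 6 |
| Latent mediator with 2 to 5 indicators | 1 to 13 |
| Five-wave cross-lagged adherence and SFD | 24 to 28 |

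**Step 3: size of a spurious indirect effect.** If M has no effect but its residual correlates r with that of Y, the fitted b tends to r × SD(Y)/SD(M). With a in SD units of M, the spurious indirect effect is a × r × 3.6. At a = 0.5:
- r = 0.1: 0.5 × 0.1 × 3.6 = 0.18 SFD
- r = 0.2: 0.5 × 0.2 × 3.6 = 0.36 SFD
- r = 0.3: 0.5 × 0.3 × 3.6 = 0.54 SFD

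For scale, the trial is designed to detect 0.7 to 0.8 SFD in total. Simulated rates of a significant indirect effect (Sobel test, two-sided 5%, 150 per arm):

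| Mediator shift | r = 0.1 | r = 0.2 | r = 0.3 |
|---|---|---|---|
| 0.5 SD | 31% | 88% | 98% |
| 0.3 SD | 13% | 50% | 69% |

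Repeat runs agreed within about three percentage points. At r = 0 the rate was 2.5% or less.

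**Step 4: whether positive degrees of freedom would help.** It depends on the restriction.
- Baseline SFD in the outcome equation only (1 df), with assumed loadings of 0.5 on a shared cause. If that cause also affects baseline SFD, the fit test rejects in 99% of datasets. If it does not, the test rejects in 5.4%, about its nominal rate, while a false indirect effect is significant in 88%.
- Mediator at 7 months affecting only 12-month SFD, with SFD residual covariances free. Moments: 6 × 7 / 2 = 21. Parameters: var(X) 1, X to M 1, X to SFD 4, M to 12-month SFD 1, mediator residual variance 1, SFD residual variances 4 and covariances 6, total 18. So 3 df. With a stable shared cause the fit test rejects in 52, 99 and 100% of trials at r = 0.1, 0.2 and 0.3, and in 5% without one.

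**The case against.** The best defence is that the zero-df model is not fixed by the plan. The primary outcome has four visits and mediators are repeated. By their titles, the methods references concern longitudinal mediation and latent variables. Planning a test against an unrestricted model also suggests that some restriction was intended. This stands to the extent that a reader might infer that every mediation model will be saturated, and the documents do not support that: several readings they allow have 1 to 28 df. Nor can one say that extra degrees of freedom never bear on mediation, since the 3-df example tests exactly mediator-outcome independence at earlier visits. The defence does not supply a restriction, however. The plan names none, and positive degrees of freedom do not guarantee detection.

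A second defence is that the false-positive rates measure confounding bias, not an effect of the fit test. That is correct: they would be the same if no fit index had been planned. A reader might infer that the plan would certify false pathways by good fit. It does not say that fit establishes a pathway; it also estimates the effects themselves, and level-one diagnostics can fail even at zero df. What remains is that neither level examines the confounding.

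The planned chi-square tests of structural invariance do not close this gap. They are there to find effect modifiers, not shared causes of mediator and outcome.

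**Conclusion.** The point holds in a limited form. In the plain reading (treatment, one observed mediator, one observed outcome, all paths free) the level-two check is empty, and no planned step addresses unmeasured mediator-outcome confounding. Under the stated assumptions a modest residual correlation gives a significant but false indirect effect in about 31, 88 and 98% of trials for a 0.5 SD mediator shift, and 13, 50 and 69% for 0.3 SD. The zero-df count is exact for that reading. The rates rest on assumed correlations and mediator shifts that the documents do not give. They show how large the exposure could be and do not predict what this trial will find.

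The mediation analysis is secondary and explanatory, and the primary mixed-model comparison of SFD is untouched. This is a cheap improvement, not a threat to the main result.

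**What to change.** In the mediation paragraph:

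1. State for each model the variables, visits, restrictions and degrees of freedom. Use the test against the unrestricted model, CFI, NNFI and RMSEA only where there are stated restrictions and positive degrees of freedom. Do not cite them as evidence for a just-identified model.
2. Estimate each indirect effect with a bootstrap confidence interval, adjusting both equations for baseline SFD and for the baseline mediator where it is measured (adherence, communication, satisfaction).
3. Where the schedule allows, use a mediator measured before the SFD visit taken as outcome. For communication and satisfaction that means the 7-month mediator with 12-month SFD.
4. State the assumption of no unmeasured mediator-outcome confounding. Report the residual correlation at which the indirect effect becomes zero, and describe pathways in that light, with no fixed pass/fail threshold.

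Adjustment alone is not enough. In one simulation with a stable shared cause and a 0.5 SD mediator shift, it reduced the spurious indirect effect from 0.18, 0.36 and 0.54 SFD to 0.15, 0.26 and 0.34. The reduction depends on how stable the mediator and the shared cause are assumed to be.

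The cost is SAP wording and a little more analysis on data already being collected. Pathway claims will be more cautious.
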